- To coordinate communications among the centers;
- To assist in training clinic staff in study procedures;
- To coordinate certification of the clinical center staff;
- To oversee the random assignment of each study participant to one of the intervention or control regimens;
- To review all study data for completeness and accuracy;
- To monitor the performance of all participating units;
- To prepare periodic reports on the performance of the clinics;
- To analyze frequency of specified events and any adverse reactions by intervention group and to report these data to the Data and Safety Monitoring Committee;
- To prepare recruitment, technical, and statistical reports for the meetings of the Steering Committee and the Data and Safety Monitoring Committee;
- To assist in the preparation of scientific reports for publication.
- 3. National Heart, Lung and Blood Institute

The NHLBI has overall responsibility for the scientific and fiscal management of TOHP. The NHLBI Project Officer is a voting member of the Steering and Executive Committees of TOHP, as well as a non-voting member of the Data and Safety Monitoring Committee.

4. Central Laboratories

All urine and blood analyses except for phospholipids will be performed by [name] at the University of Minnesota School of Public Health in Minneapolis, which will also store additional plasma and serum samples for possible later analyses. Blood phospholipid analyses will be performed by [name] at the Channing Laboratory in Boston.

Study Administration

The administrative structure of TOHP consists of a series of committees and subcommittees which include representatives from all the participating units.

1. Steering Committee

The Steering Committee is the central governing body of TOHP. It is made up of the principal investigators, interventionists, and coordinators from each of the clinical centers as well as representatives from the CC and NHLBI. Each participating unit has one vote normally cast by the Principal Investigator. The Steering Committee meets at least semi-annually to review the progress of the trial. Each center is required to be represented at each meeting by at least the Principal Investigator (or designated co-investigator) and one other representative from that clinic. The Study Chairman serves as chairman of the Steering Committee.

The meetings of this group are a forum for the discussion of study problems as well as the dissemination of information. The face-to-face discussion of trial activities, along with opportunities to interact on a personal level contribute to the development of rapport among study collaborators that facilitates the operation of a multicenter clinical trial.

Subcommittees and working groups of the Steering Committee are formed as needed. There are five subcommittees of the Steering Committee that were formed initially to assist in the planning process for TOHP and have ongoing charges during the study itself. These are summarized below.

The Design and Analysis Subcommittee is primarily responsible for recommending to the Steering Committee overall design features, e.g., sample

sizes, blinding, and stratification; for proposing to the CC specific data analyses for the study; for reviewing requests from investigators for data analyses and recommending priorities for analysis; and for reviewing proposals for ancillary studies and recommending approval or disapproval to the Steering Committee for their review and vote.

The Eligibility and Recruitment Subcommittee recommends the inclusion and exclusion criteria for participant eligibility and is responsible for development of strategies and resources to aid the clinical centers in effective and efficient recruitment. It is also responsible for reviewing recruitment reports from the CC in order to identify problems and propose solutions on a clinic-by-clinic basis.

The Interventions Subcommittee develops intervention methods and materials, monitors compliance outcomes, and if necessary, proposes modifications of the intervention protocols for review and approval by the Steering Committee. This group also provides advice, as requested, to the Data Collection and Quality Assurance Subcommittee concerning methods for assessing adherence to the TOHP interventions.

The Data Collection and Quality Assurance Subcommittee recommends to the Steering Committee the data set to be collected from TOHP participants, including review of data forms, and is responsible for recommending to and collaborating with the CC in implementing quality assurance programs for: monitoring the performance of clinic personnel in adhering to the study protocol and Manual of Operations; certification and recertification procedures for both clinical center staff and equipment; and monitoring the quality of laboratory data.

The Publications and Presentations Subcommittee is responsible for establishing and implementing procedures for review of publications and presentations of TOHP materials and data. In addition to assuring accurate and timely presentation of pertinent information to the scientific community, an objective of the subcommittee is to encourage all investigators to have the opportunity to participate in presentation and publication of study-wide data.

In addition, at the conclusion of the planning phase, a sixth subcommittee was constituted. The Clinic Coordinators Subcommittee is composed of one

individual from each clinical center who is responsible for assisting the Principal Investigator in organizing the center staff, facilities, and tasks, as well as representatives from the CC. This group will meet in conjunction with the semiannual Steering Committee meetings and will function via correspondence and conference calls in the interim periods. vities of this subcommittee include dissemination of information received from the CC and other trial components to appropriate clinic staff; assisting in the design and implementation of procedures for the flow of patients through the clinics and flow of data to the CC; identification and resolution of problems in organization of staff and physical facilities to maintain separation of intervention and data collection; assisting in the development of systems (such as use of case managers) to encourage high attendance and compliance rates; provision of information to the CC on a regular basis regarding the overall functioning of the clinic; and provision of input to the CC on the design and implementation of quality control monitoring and error correction procedures.

2. Executive Committee

The TOHP Executive Committee, is made up of the chairmen of the five sub-committees of the Steering Committee, the NHLBI Project Officer, the CC director, and the study chairman. This group discusses and helps to formulate and implement all Steering Committee decisions related to the conduct of TOHP within the guidelines established by the protocol.

Specific functions of the Executive Committee include:

- Resolving any operational problems that arise between Steering
 Committee meetings, consulting with the principal investigators if appropriate;
- Advising and assisting the CC on operational matters;
- Preliminary review of the performance of all participating centers on the basis of reports provided by the CC.

The Executive Committee meets in advance of the meetings of the Steering Committee and as necessary on other occasions.

11/7/88

3. Data and Safety Monitoring Committee

The Data and Safety Monitoring Committee (DSMC) is responsible for reviewing the initial study protocol, for assessing accumulating study data for adverse and/or beneficial intervention effects, and for seeing that risks to subjects are minimized. As part of this responsibility for minimizing risk to participants, the DSMC reviews procedures for data surveillance to assure that these are sufficient to identify the occurrence of adverse events in any intervention group. This review includes receiving monitoring reports prepared and supplied by the staff of the CC for evidence of adverse or beneficial intervention effects. After review of each report, the DSMC is responsible for making specific recommendations to the Steering Committee and the NHLBI about whether to continue the study, with or without changes in the protocol, or to stop the trial. The DSMC is also charged with advising the Steering Committee and NHLBI on whether to proceed with Phase II of TOHP. Votes at meetings are identified and recorded by individual response.

-62-

The DSMC members are appointed by the NHLBI Project Office based on consultation with the Executive Committee. The voting members represent skills in cardiovascular disease epidemiology, trial methodology, biostatistics, nutrition, behavioral science, and bioethics. The study chairman, CC director, and NHLBI Project Officer serve as non-voting members. A complete membership listing of this committee is contained in Appendix B.

Members of the DSMC are expected:

- To acquire a detailed knowledge of the TOHP design and goals;
- Attend two meetings of the DSMC each year, with additional meetings as needed during periods of active decision making;
- To study data monitoring reports and other material submitted by the CC or the Data Collection and Quality Assurance Subcommittee;
- To suggest analyses to be included in data monitoring reports;

- To communicate in a timely way with the Institute and principal investigators, with an emphasis on two-way communications.

Members of the DSMC may be invited to attend meetings of the Steering Committee at the discretion of the Steering Committee Chairperson.

4. Study Chairman

The study chairman, appointed by the NHLBI Project Office, has a major responsibility for the scientific direction of TOHP and proper implementation of the decisions made by the Steering Committee. He is informed on all aspects of study operations and takes action as necessary to insure the smooth operation of the trial. He also serves as chairman of the Executive Committee and the Steering Committee for the trial.

ANCILLARY STUDIES

An ancillary study is a research study, the principal investigator of which is at least a TOHP co-investigator and which must be approved by the principal investigator. An ancillary study is characterized by one or more of the following:

- 1. Observations/procedures supplemental to the TOHP protocol are implemented in all or a subgroup of participants according to a set protocol;
- 2. Additional work by or information from the TOHP coordinating center on screenees or participants is required; or
- 3. Investigative work on the methodology of TOHP is involved.

Ancillary studies are encouraged, for they can enhance the value of TOHP and insure the continued interest of the many capable investigators involved.

Request for Approval of an Ancillary Study

An investigator who wishes to undertake an ancillary study must prepare a formal research proposal describing the proposed study. This proposal should

contain statements on objectives, background, methods of study and feasibility, as outlined in the next section.

These proposals for ancillary studies are to be submitted to the Design and Analysis Subcommittee for preliminary review. Copies of the proposal should be made available to all members of the subcommittee one week prior to the meeting at which it is to be considered. The primary objective is to review the compatibility of the ancillary study with the existing study and its priorities. Any proposed procedure that would interefere with one or more of the procedures of the TOHP protocol or would result in a decrease in the compliance of the participants in TOHP is sufficient reason for the disapproval of the proposed ancillary study. Questions on the proposal are referred back to the applicant for amplification, clarification, or withdrawal of the request. The Design and Analysis subcommittee will make a recommendation to the Steering Committee on approval or disapproval of the proposed study. A proposal that has received conditional approval must be resubmitted to the Design and Analysis Subcommittee for final consideration.

Those proposals that are judged compatible with the TOHP protocol are submitted to the Data and Safety Monitoring Committee (DSMC) for review. After this final review of the proposal, the NHLBI project office will prepare a statement of the DSMC's consensus, including anyreservations or objections, and forward it to the investigator who requested approval of the ancillary study.

Form of Protocol for an Ancillary Study

A proposal for an ancillary study that is submitted to Design and Analysis should include information on the following areas:

- A. Objectives
- B. Background
- C. Methods of Study
- D. Effects on TOHP
 - Financial
 - 2. Logistic/Study Flow
 - 3. Scientific
 - 4. Compliance

- E. Source of Support
- F. Investigators and Clinics Involved
- G. Length of Time Required for Procedures
- H. Other Ancillary Studies that Clinics are Involved In

Some ancillary studies may require the CC to perform statistical analyses or make available to the investigator data that are not already available. In either or both cases, the proposal should be accompanied by a statement from the CC indicating the commitment of its services to the study.

If additional funding is requested, a proposed budget following the usual NIH format must be submitted.

Funding of an Ancillary Study

If no additional funds are required, the investigator may proceed with the ancillary study as soon as written approval from the project office has been received. If additional funds are requested in the proposal, the project officer will submit a written summary of the decisions of the Steering Committee to the investigator.

Publication and/or Presentation of Ancillary Study Results

All manuscripts or presentations for scientific meetings that are based on ancillary studies making use of data collected according to the TOHP protocol must be reviewed and approved by the Publications and Presentations Subcommittee before publication or presentation.

PROTOCOL CHANGES

Any change to the protocol must be submitted in writing to the Steering Committee and approved by a two-thirds majority of all voting members (one vote for each PI, NHLBI Project Officer, and Coordinating Center Director). Alternatively, any protocol change which arises in the course of a Steering Committee meeting and is thus not in written form requires unanimous approval.

-66- 11/7/88

REFERENCES

- 1. US DHHS. Health United States. Public Health Service, National Center for Health Statistics, DHHS Publ No (PHS) 85-1232. Hyattsville, MD: 1984.
- 2. Pooling Project Research Group. Relationship of blood pressure, serum cholesterol, smoking habit, relative weight and ECG abnormalities to incidence of major coronary events. Final report of the Pooling Project. J Chron Dis 1978; 31:201-62.
- 3. Kaplan NM. Clinical Hypertension. 4th edition. Baltimore: Williams and Wilkins, 1986.
- 4. Veterans Administration Cooperative Study Group on Antihypertensive Agents. Effects of treatment on morbidity in hypertension: Results in patients with diastolic blood pressure averaging 115 through 129 mm Hg. JAMA 1967; 202:1028-34.
- 5. Veterans Administration Cooperative Study Group on Antihypertensive Agents. Effects of treatment on morbidity in hypertension: II. Results in patients with diastolic blood pressure averaging 90 through 114 mm Hg. JAMA 1970; 213:1143-52.
- 6. Hypertension Detection and Follow-up Program Cooperative Group. Five-year findings of the Hypertension Detection and Follow-up Program. I. Reduction of mortality of persons with high blood pressure, including mild hypertension. JAMA 1979; 242:2562-71.
- 7. Australian National Blood Pressure Study Management Committee. The Australian therapeutic trial in mild hypertension. Lancet 1980; 1:1261-7.

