During the intensive intervention phase, subjects will attend weekly group meetings for 3 months (14 sessions). These 90-minute meetings will be led by two staff members. The groups will consist of about 10 subjects plus support people invited by the subjects. Each session will consist of at least four components including nutrition, exercise, behavioral selfmanagement, and social support. At the midpoint of each intervention session, the group will be divided into two small groups for intensive review of each person's progress and plans for the next week. will display their weight change/exercise graph and discuss their selfmanagement efforts for the past week. Leaders will guide the discussion toward individual problem-solving and developing specific and detailed action plans, and the small group meetings will end with each subject describing their behavioral goals and action plans for the next week. Initially, participants will be asked to begin exercising moderately 2-3 times per week, and supervised exercise sessions will begin at the third group meeting. An outline of the intensive intervention sessions is shown in Table 9.

After completing the intensive phase, subjects will be asked to attend monthly meetings for the remainder of the intervention period. During this maintenance phase, several initial intervention groups will be combined into two follow-up groups, each of which will meet monthly. Subjects will be given the option of attending one or both of the monthly follow-up meetings. The format of the maintenance meetings will be similar to the initial intervention meetings. These meetings will feature formal presentations and group discussions on selected nutritional and behavioral change topics as well as small group meetings at every session. Attendance will be encouraged by the addition of special events such as cooking demonstrations and special dinners.

Relapse prevention will be particularly important during the maintenance phase. Subjects will prepare for potential relapse situations by:

- Identifying difficult situations in which relapse is likely to occur;
- b. Developing a reasonable coping strategy and alternative behavior; and
- c. Practicing the alternative behavior in response to a simulation of the trigger situation.

4. Measures to Assess and Enhance Compliance

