The intervention is primarily group-oriented and consists of 23 sessions. The initial eight sessions are weekly, followed by four biweekly, eight monthly, and three bimonthly sessions. There are two components to this program: (a) interventions to increase awareness of stress level indicators (physical sensations, thoughts, feelings, images, activities), and (b) interventions to lower stress level. An outline of the intervention sessions is shown in Table 10.

The first task of intervention is to build awareness in individuals of event-to-event changes in their stress indicators. This will be accomplished by presentation of case examples, group discussion of participants' experiences, and daily self-monitoring. Following the development of this increased awareness of changes in stress indicators, participants will be encouraged to discover the connections between

changes in their stress signs and related patterns of events and cognitions using the same techniques.

As individuals become aware of how stressful events and stress responses are linked, intervention will focus on training in various components of stress level reduction. A key component will involve training in a variety of relaxation methods, which will increase the likelihood that all participants will find a method they can employ successfully and enjoy. While the variety helps maintain participant interest, all of the methods are variations on the same theme of staying more relaxed and comfortable throughout the day. Relaxation training can influence a number of the contributors to excessive stress levels by reducing excessive autonomic arousal and reactivity, as well as increasing sensitivity to changes in stress indicators. A second component will involve training in methods of managing reactions to stressful situations. This component is similar to anger and anxiety management training and focuses on rehearsing staying calm and relaxed in stressful situations. A third component will involve training in methods of altering cognitive contributions to stress. Finally, the fourth component will involve training in methods of managing stressful situations, focusing on methods of communication, assertiveness, and time management.

4. Measures to Assess Compliance

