with the variance components defined as previously. These data suggest true four-year and one-year correlations of 0.85 and 0.91, respectively. Interpolating to 6 and 18 months, the true correlations in TOHP are estimated to be 0.92 and 0.90, respectively. Given three visits with three measurements each, we would expect to observe correlations of approximately 0.84 (6 months) and 0.83 (18 months). These figures lead to estimated variances for the change in means of 38.03 (standard error = 6.17) for 6 months and 40.41 (standard error = 6.36) for 18 months of observation.

Allocation of Subjects

Clinic-specific allocations are presented in Table 1.

Power_Calculations

Power calculations assume a two-sided test with significance level 0.05 and use the following formula:

Power =
$$1 - \Phi \left[z_{1-\alpha/2} - \frac{d}{\frac{\sigma^2}{n_1} + \frac{\sigma^2}{n_0}}\right]$$

where: $\Phi[\]$ = the area to the right of [] on the standard normal curve

 $z_{1-\alpha/2} = 1.96$

d = the difference in BP change between the intervention and comparison groups

 σ^2 = 6.172 for supplements and 6.362 for lifestyles

 n_1 = the number in the active intervention group

 n_0 = the number in the control group

The estimated powers associated with the expected numbers in the proposed study design are given in Table 12. All tests will have at least .90 power to detect a 2 mm Hg change in DBP.

POWER CALCULATIONS: SBP

Estimate of Variance

The same methods used for DBP have been used to estimate the components of variance for SBP. The variance of the mean BP (\vec{x}) at either baseline or termination can again be written as:

$$V_{(\vec{x})} = \sigma^2 = \sigma^2_p + \sigma^2_A/N + \sigma^2_e/NK$$

where: σ^2_{p} = between-person variance

 σ^2 A = between-visit variance

 σ^2 = within-visit variance

N = number of visits = 3

K = number of measurements per visit = 3

The variance of the difference between the baseline and termination values is a function of σ (defined above) and the tracking correlation (the variation in BP over time):

$$V(\overline{x}_1 - \overline{x}_2) = 2\sigma^2(1-\rho)$$

where:

- mean SBP at baseline

- mean SBP at termination

- the observed tracking correlation of the BP means over an average of 18 months of follow-up for the lifestyle interventions and six months of follow-up for the supplement interventions

Estimating the components of the variance of the mean BP at either base-1. line or termination

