The primary outcomes of interest for the lifestyle interventions is the difference between changes in mean DBP from baseline to 18 months between the intervention and comparison groups, with the BP for each participant being determined from nine readings (three readings at each of three visits). The primary endpoint for the supplement interventions is change in DBP from baseline to six months. In the crudest level of analysis, mean change in DBP in each of the actual intervention groups with the control group will be compared in the context of the one-way analysis of variance. At a second level, mean change in DBP between each of the active intervention and control groups will be compared after controlling for clinic. This will be accomplished using multiple regression methods introducing dummy variables for

clinic and intervention group. In addition, more refined analyses will be performed to adjust for other covariates, such as mean initial DBP, age, and sex.

Secondary endpoints in the trial, including changes in SBP and the development of hypertension, will also be examined. The former will be evaluated in the same manner as changes in DBP described above. The development of hypertension will be defined as either going on antihypertensive medications during the course of the trial or attaining a mean DBP greater than or equal to 95 mm Hg based on nine readings over three visits at any point in the trial.

While change in DBP from baseline to termination is the primary outcome of interest, there will also be the opportunity to examine BP measurements taken throughout the follow-up period. In particular, slopes of BP over time will be compared based on available data per participant. Slopes in different treatment groups will also be compared using analysis of variance and regression methods as discussed above. More sophisticated methods of longitudinal data will be utilized to characterize more complex changes in BP over time (105-107). In addition, BP change from baseline to the 12-month follow-up point for lifestyles interventions will also form the basis for planning for Phase II of TOHP.

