Session 9

Review of First Food Exchange Diaries Healthy Eating (U.S. Dietary Goals) Individual Planning Supervised Exercise

Session 10

Food Exchange Scoring System Self-reinforcement techniques Individual Planning Supervised Exercise

Sessions 11-14

Outlines to be developed. All of these sessions will include: Individual Planning Supervised Exercise

-FINAL TOHP STRESS MANAGEMENT PROGRAM COMPONENT SEQUENCING

MONTH	SESSION	TYPE	Weekly Sessions	
M01	01		Individual orientation & intervention data collection	-
M01			Group building + Slow-Paced Breathing	-
1	03	1 1	Bernstein & Borkovec Progressive Muscle Relaxation (B&B PMR) #1	1 1
	[04		B&B PMR #2: Emphasis on minimal tension & applications	1
	05		Relaxation using Imagination	1 (
M02			Applied Relaxing Imagination: Desensitization	1
M02			Applied Relaxing Imagination: Positive Covert Rehearsal	MI
M02	08	G	Clinically Standardized Meditation (CSM)	
			Biweekly Sessions	
М03	09	G	Time Management #1	
	10			M2
M04	11	G		
M04	12	G	Changing Stressful Thinking Patterns #1	
			Monthly Sessions	
MO5	13	G	Changing Stressful Thinking Patterns #2	1
M06	14	I	Individual session. Focus: Long term maintenance & applied skills	
	15			1 1
M08	16	G	Positive Cognitive Coping Strategies	1
	17			1.3
M10	18	G	Active Listening + Assertiveness Training #2	op [
			Anger Management #1	M4
M12	20	G	Anger Management #2	
			Bimonthly Sessions	
M14	21	G	General Problem Solving Session #1	45
	22		General Problem Solving Session #2	146
M18	23	G	General Problem Solving Session #3	M 7

Type: G or I: Type of session, group or individual

M1, etc.: Represents 10 min. segment on long term maintenance

Table 11

DOSAGES AND NUMBER OF DAILY PILLS REQUIRED FOR TOHP SUPPLEMENTS INTERVENTIONS

Supplement	Dosage/Day	Dosage/Pill	Pills/Day
Calcium carbonate	1000 mg	500 mg	2
Magnesium diglycine	360 mg	60 mg	6
Potassium	60 mmoles	20 mmoles	3
Fish oil*	3000 mg	500 mg	6

^{* 1000} mg capsule of Promega contains 500 mg of fish oil.

Table 12
SAMPLE SIZE AND POWER ESTIMATES: DBP

	Size of Comparison		Average	Δ for	
Intervention	Active	Control	Expected Follow-up	80% Power (mm Hg)	$\Delta = 2 \text{ mm Hg}$
Sodium Restriction	327	416	18 months	1.32	.99
Weight Reduction	308	232	18 months	1.55	. 95
Stress Management	242	319	18 months	1.66	. 92
Calcium	237	234	6 months	1.60	.94
Magnesium	227	234	6 months	1.61	. 94
Potassium	207*	203*	6 months	1.70	.91
Fish oil	199*	203*	6 months	1.72	. 90

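### The lifestyle arms are treated in shared groups, but the power formula and the DBP analysis treat participants as independent; if outcomes within a group are positively correlated, the lifestyle standard errors are too small

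*Protocol*

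**What the plan says.** **Delivery.** All three active lifestyle programs work mainly through shared sessions (Protocol, Intervention Methods).

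- Weight reduction has 14 weekly meetings led by two staff members: "The groups will consist of about 10 subjects plus support people invited by the subjects". In maintenance, several initial groups are combined into two follow-up groups, and participants may attend either or both.
- Sodium reduction has eight group meetings and two individual sessions in its intensive phase. No group size is stated.
- For stress management, "The intervention is primarily group-oriented and consists of 23 sessions". No group size is stated.
- Lifestyle controls receive no active intervention and attend no groups.

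**Analysis.** Data Analyses starts with a one-way analysis of variance. At the next level, "mean change in DBP between each of the active intervention and control groups will be compared after controlling for clinic", using dummy variables for clinic and for treatment arm. Later refinements add covariates such as initial DBP, age and sex.

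**Power.** Power Calculations: DBP says: "Power calculations assume a two-sided test with significance level 0.05 and use the following formula". The formula divides one participant-level variance by the number in each arm. For the lifestyle arms the variance of change is given as "40.41 (standard error = 6.36) for 18 months of observation". The section concludes: "All tests will have at least .90 power to detect a 2 mm Hg change in DBP".

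**The concern.** Individual randomization makes the arms comparable, but it does not keep participants independent once treatment begins. People taught together for months by the same leaders share whatever makes one group do better or worse than another. The protocol expects this in part: the stress section credits the group experience itself with faster learning and enthusiasm, and the weight-loss session outline includes building cohesion in the first meeting.

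The result is a partially nested design, with clustered active arms and an unclustered control. The stated ANOVA, regression and power formula all assume independent participants. A clinic dummy removes differences between clinics, but not differences between two session groups in the same clinic and arm.

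At stake are the width of the confidence intervals and the true size of the 5% test for the three lifestyle comparisons. Any positive correlation moves both in the anti-conservative direction. The supplements arms are not treated in groups, so uncorrected lifestyle estimates would also look more precise relative to supplement estimates than they are. These results feed the planning of Phase II.

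**Working it through.** **Inputs from the protocol.** SD of 18-month DBP change 6.36 mm Hg; two-sided alpha 0.05; difference 2 mm Hg; active and control numbers from Table 12: weight 308/232, sodium 327/416, stress 242/319. Group size of about 10 is stated for weight.

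**Assumptions.** ICC 0 to 0.05, because none is given. Group size m = 10 for sodium and stress. Total variance is held at 6.36². A normal approximation is used, which ignores the limited degrees of freedom from about 31, 33 and 24 groups (308/10, 327/10, 242/10).

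**Step 1: reproduce Table 12 under independence.** SE = 6.36 × √(1/n1 + 1/n0); power = Φ(2/SE − 1.96); detectable difference at 80% power = SE × (1.96 + 0.84). The printed formula shows no square root in the denominator, possibly lost in text extraction; the figures below need it.

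- Weight: SE = 6.36 × √(1/308 + 1/232) = 0.553; power .951; detectable difference 1.549. Table 12 prints .95 and 1.55.
- Sodium: SE = 0.470; power .989; detectable difference 1.317. Table 12 prints .99 and 1.32.
- Stress: SE = 0.542; power .958; detectable difference 1.519. Table 12 prints .92 and 1.66, which do not follow from 242/319. That is a separate discrepancy.

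The weight and sodium rows reproduce with no allowance for clustering.

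**Step 2: add clustering in the active arm only.** Design effect DE = 1 + (m − 1) × ICC; SE = 6.36 × √(DE/n1 + 1/n0); ratio = clustered SE / independent SE; true size of the unadjusted test = 2 × [1 − Φ(1.96/ratio)].

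Worked case, weight at ICC 0.05: DE = 1 + 9 × 0.05 = 1.45. SE = 6.36 × √(1.45/308 + 1/232) = 0.604. Ratio = 0.604/0.553 = 1.092. Size = 2 × [1 − Φ(1.96/1.092)] = 7.3%. Power = Φ(2/0.604 − 1.96) = .912. The 95% half-width goes from 1.96 × 0.553 = 1.08 to 1.96 × 0.604 = 1.18 mm Hg.

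Each cell below gives SE ratio; true size; power at 2 mm Hg, with m = 10.

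| ICC | DE | Weight | Sodium | Stress |
|---|---|---|---|---|
| 0 | 1.00 | 1.000; 5.0%; .951 | 1.000; 5.0%; .989 | 1.000; 5.0%; .958 |
| 0.01 | 1.09 | 1.019; 5.4%; .944 | 1.025; 5.6%; .986 | 1.025; 5.6%; .949 |
| 0.02 | 1.18 | 1.038; 5.9%; .936 | 1.049; 6.2%; .982 | 1.050; 6.2%; .940 |
| 0.05 | 1.45 | 1.092; 7.3%; .912 | 1.119; 8.0%; .967 | 1.121; 8.0%; .909 |

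**Step 3: where the power claim would fail.** At m = 10, power drops below .90 only above an ICC of about 0.063 (weight), 0.058 (stress) and 0.143 (sodium).

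**Step 4: sensitivity to the undocumented group size.** At ICC 0.05 the sodium and stress ratios are both 1.055 with m = 5 (size 6.3%). With m = 15 they are 1.180 and 1.182 (size 9.7%), and power is .950 for sodium and .877 for stress.

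**The case against.** The strongest reply is that the harm is conditional and may be small. The protocol gives no ICC. At zero nothing is wrong, and at 0.01 the weight standard error rises by only 1.9%. Sodium participants also have individual counseling and self-directed work, which may weaken any group effect. Random-effect structure is often left to an analysis plan, and one may exist. The first three points stand and limit the size of the finding. The last does not remove it, because the protocol itself states the model and the variance formula, and both assume independence. The cited longitudinal methods concern blood pressure over time, not session groups.

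Four stronger readings are tempting, and the documents do not support them.

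- A reader might infer groups of about 10 in all three arms. That size is stated for weight only.
- A reader might infer that the trial is underpowered. At m = 10 the .90 claim holds over the whole assumed range. The printed stress power of .92 cannot be called optimistic on this ground either: with 242/319 the recomputed power is .940 at ICC 0.02 and .909 at ICC 0.05, so .92 lies inside the clustered range.
- A reader might infer that merging weight groups in maintenance makes matters worse. Larger clusters raise the design effect only if the ICC stays the same. Attendance at either or both follow-up meetings mixes membership and may dilute the correlation, so the direction is not established.
- A reader might infer that the open design compounds the error. Blood pressure observers are to be blinded and kept apart from intervention delivery; observer bias is a different question from clustering.

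**Conclusion.** The point holds in conditional form. The plan treats group-delivered lifestyle participants as independent, and neither the clinic dummies nor the listed covariates repair that. If session-group outcomes are positively correlated, the stated standard errors are too small.

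For ICC 0 to 0.05 and m = 10, the correct standard error exceeds the planned one by 0-9% for weight and 0-12% for sodium and stress. The nominal 5% test runs at 5.0-7.3% and 5.0-8.0%. The ICC is an assumption throughout; the group size is documented for weight and assumed for the other two.

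Recomputed power at ICC 0.05 and m = 10 is .91 (weight), .91 (stress) and .97 (sodium), so the claim of at least .90 survives there and no change in sample size follows. For stress this depends on the assumed group size, as the m = 15 case shows. The consequence is for intervals and type I error. The correction is worth making because it is cheap and the error can run in only one direction when the correlation is positive.

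**What to change.** 1. Record the initial session group of every active lifestyle participant, and the maintenance group or groups where relevant. Table 2 lists no such item, although the clinics will know the membership.
2. Fit the lifestyle DBP regression with a random effect for session group in the active arm only, treating controls as singletons and keeping the clinic dummies. Alternatively, keep the regression and use cluster-robust standard errors with a small-sample correction, since there may be only some 24 to 33 groups per arm.
3. Optionally, add a note to Table 12 showing lifestyle power over ICC 0 to 0.05, with the assumed group size stated for sodium and stress.

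The cost is one recorded variable and one extra model term. The downside is intervals wider by roughly 10% at the top of the assumed range (9% for weight, 12% for sodium and stress), and by little or nothing if the correlation proves negligible.
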